 - c) Assessment for re-intervention or re-surgery for recurrence or persistence of POP: No need for pessary use or additional surgical treatment for prolapse at any time after the initial procedure
 - d) No mesh / suture exposure
2. Assessment of participant changes in QoL, symptom bother, and sexual functioning at 1 year compared to baseline^{30,31}:
 - PFDI 20-Pelvic Floor Distress Inventory
 - PFIQ-7-Pelvic Floor Impact Questionnaire
 - PISQ-IR-Pelvic Organ Prolapse/Urinary Continence Sexual Questionnaire

3. Assessment of procedure-related or pelvic floor-related adverse outcomes in each group as classified according to the Clavien-Dindo surgical complication grading scale²⁹. Adverse events will be assessed intra-operatively, at 6 weeks, 6 months, and 1 year postoperatively.

STATISTICAL CONSIDERATIONS

Statistical Methods

Data analyses will include t-tests for continuous data, chi-square or Fisher's exact for categorical data, and multi-variable regression to assess the effects of any bivariate analyses found to have a positive relationship. Confidence intervals will be reported for continuous data and will be included in the assessment and reporting of outcomes. When the data are analyzed, both chi square and Fisher's exact analyses are performed and the appropriate test and associated p value will be used based on the proportion of samples with input less than 5% of the total population. Those with a small output will utilize Fisher's exact.

The data will be analyzed as Intent to Treat. Missing data may occur if subjects fail to return for follow up, thus we plan to over-recruit in order to account for a 20% drop-out rate. Since study participants are undergoing surgery, they are more likely to return for their follow-up visits since these are part of their standard post-operative care. This will decrease the rate of drop-outs. The fact that this is an RCT will minimize the chance of a differential drop-out rate between the groups.

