The rate of reported mesh exposure varies greatly from 0-27%, as discussed in our Background section on page 2 of the Investigator Protocol. Based on published data both at our institution and elsewhere in the literature, we determined that a 10% and 1% rate of mesh exposure in the two groups is both supported by data and clinically relevant, thus we are estimating a 9% difference in mesh erosion rates between the two groups: 1% vs 10%. This is a clinically significant difference that would affect a change in clinical practice.

Sample Size

The power calculation was performed using the statistical computation software Epi Info™ 7.1.3.10, developed on 3/11/14. It is a trademark of the Centers for Disease Control and Prevention and uses chi square for its computation of sample size for studies based on categorical data comparison such as the current study.

We are planning a study of independent cases and controls with 1 control(s) per case. Prior data indicate that the mesh exposure rate among controls is 10%. If the mesh exposure rate for experimental subjects is 1%, we will need to study 80 experimental subjects and 80 control subjects to be able to reject the null hypothesis that the failure rates for experimental and control subjects are equal with probability (power) 0.8. The Type I error probability associated with the test of this null hypothesis is 0.1. The alpha of 0.1 is based on a one-sided hypothesis, estimating that mesh exposure rates will be higher in the study arm using permanent suture compared to the study arm using absorbable suture. We will use an uncorrected chi-squared statistic to evaluate this null hypothesis. We plan to enroll a total 200 subjects across sites to account for up to 20% loss to follow up, thus the use of chi square is appropriate given the adequately large sample size.

We feel the sample size is appropriate based on our sample size calculation, taking into account the estimated rates of mesh exposure in the two groups, as well as our clinical judgment of the number of procedures that are performed each year at the study sites. In the past year each

study site has performed 50 cases, for a total of 200 cases at all combined sites. Therefore our sample size of 100 subjects per study arm is feasible for completion in the time allotted.

Primary Hypothesis

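### For mesh/suture exposure, an open-ended bivariate screen chooses the regression terms when only about 9 to 11 events are expected, and an ordinary logistic arm estimate would often be non-finite

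*Combined protocol and SAP*

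**What the plan says.** Under Statistical Considerations, the Statistical Methods section lists t-tests, chi-square or Fisher's exact tests, and "multi-variable regression to assess the effects of any bivariate analyses found to have a positive relationship". It does not define a positive relationship. It gives no significance threshold, candidate covariates, limit on their number, model type or outcome for the regression, and it does not say whether arm or site is always included.

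The Sample Size section assumes 10% exposure among controls and states: "If the mesh exposure rate for experimental subjects is 1%, we will need to study 80 experimental subjects and 80 control subjects". Enrolment is 200, to allow for up to 20% loss. For the primary null hypothesis it says: "We will use an uncorrected chi-squared statistic to evaluate this null hypothesis". The regression is therefore not the primary test.

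The Randomization section stratifies by site, with five sites.

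**The concern.** There are two separate difficulties, both confined to the exposure outcome.

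The first is the selection rule. Terms that look positive in one pass through the data are refitted to the same data. The nominal p-values and confidence intervals then ignore the selection, and with so few events there is little room for more than one term.

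The second is sparsity. If the absorbable arm has no exposures, ordinary logistic regression has no finite arm odds ratio. The Background makes this a realistic outcome: in the section on the rationale for studying suture material, both retrospective series of delayed absorbable monofilament suture report zero exposures (0% against 3.7%, and none in 67 women).

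At stake are the adjusted suture effect and any risk-factor statements for exposure. Regression is the only method the section names that would give an adjusted effect.

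**Working it through.** **Inputs.** From Sample Size: control rate 0.10, absorbable rate 0.01, 80 evaluable per arm, 100 per arm enrolled, power 0.8, alpha 0.1. From Randomization: five sites.

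**The plan's own figure.** The pooled-variance formula for two proportions is

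n = [z_α √(2 p̄ q̄) + z_β √(p₁q₁ + p₂q₂)]² / (p₁ − p₂)²

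Here p̄ = 0.055, 2 p̄ q̄ = 0.10395 and p₁q₁ + p₂q₂ = 0.0999.
- Two-sided 0.10 (z_α = 1.645): (0.530 + 0.266)² / 0.0081 = 78.3, so 79 per arm. The stated 80 is reproduced to within one.
- One-sided 0.10 read literally (z_α = 1.282): 57 per arm. That mismatch is a separate matter; only the 80 and the two rates are used here.
- Loss to follow-up: 160 / 0.80 = 200, as stated.

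**Expected exposures.**
- 80 per arm: 80 × 0.10 + 80 × 0.01 = 8 + 0.8 = 8.8 (5th to 95th percentile 4 to 14).
- 100 per arm: 10 + 1 = 11.0 (6 to 16).
- Events per term at 8.8: 8.8 with one term, 4.4 with two, 2.9 with three.

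**Probability of no event in the absorbable arm**, (1 − p)ⁿ:

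| True absorbable rate | 80 per arm | 100 per arm |
|---|---|---|
| 0.5% (assumed) | 67% | 61% |
| 1% (plan) | 45% | 37% |
| 2% (assumed) | 20% | 13% |
| 3% (assumed) | 9% | 5% |
| 5% (assumed) | 2% | 1% |

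An empty control arm is negligible (0.90⁸⁰ = 0.0002).

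**If arm enters only because its own bivariate test was significant.** Enumerating all tables at the planning rates, the absorbable arm is empty in 47% to 60% of such trials at 80 per arm and 38% to 45% at 100. The range covers chi-square at one-sided 0.10 through Fisher at two-sided 0.05.

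**What the screen adds.** Assume eight binary covariates with no true effect, prevalence 10% to 50%, 80 per arm and 2,000 simulated trials.
- At least one passes in about 20% of trials at p < 0.05 and 39% at p < 0.10.
- Two or more pass in about 2% and 9%.
- A non-finite estimate from arm or a selected covariate occurs in 48% to 49%, against 45% from arm alone.

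The empty arm therefore causes nearly all the non-finite estimates, and the screen adds 3 to 4 points.

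**Site.** Entering arm and five sites as ordinary terms gives at least one non-finite coefficient in 74% of simulated trials at 80 per arm and 60% at 100.

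**Primary test with an empty arm.** For 8/80 against 0/80, the uncorrected chi-square is 160 × (8 × 80 − 0 × 72)² / (8 × 152 × 80 × 80) = 65,536,000 / 7,782,400 = 8.42. The test works normally.

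**The case against.** The strongest reply is that the plan commits to very little here. It names no threshold, model or regression outcome, does not say that arm is included, and may mean only that positive bivariate findings get an adjusted follow-up. That stands: the non-finite result is conditional on ordinary maximum-likelihood logistic regression of exposure with arm in the model.

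A reader might infer that the model will certainly be overfitted. The documents do not support that. The number of terms that would enter is unknown, and with null covariates two or more enter in only about 2% to 9% of simulated trials. True risk factors would raise this, but the documents give no basis for saying by how much.

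A reader might also infer that the estimate fails about half the time, or that the screen is to blame. Unconditionally the range is 37% to 45%. It exceeds 45% only at 80 per arm and only after conditioning on a significant arm effect or adding further terms. It falls quickly as the true absorbable rate rises, and the Sample Size discussion itself notes reported rates from 0% to 27%. Removing the screen alone would leave most of the problem.

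Nor does the point undermine the primary conclusion or the whole analysis plan. Chi-square and Fisher's exact test both work with an empty arm. The sentence also covers questionnaire scores and composite success, and the 9-event count applies to exposure, not to those outcomes.

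What survives is that a data-driven rule is stated. Followed on this outcome, it yields post-selection inference, with no provision for sparse events.

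**Conclusion.** The point holds for the exposure outcome, as a minor one. With about 9 to 11 expected events, selecting regression terms by bivariate result gives p-values and intervals that do not carry their nominal meaning, and it risks overfitting if more than about one term enters. Separately, an ordinary logistic arm odds ratio would be non-finite in about 37% to 45% of trials.

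These sizes rest on the plan's 10% and 1% rates and on 80 to 100 evaluable per arm; the second also assumes maximum-likelihood logistic regression with arm included. If the true absorbable rate is 2% or more, the non-finite proportion is 20% or less.

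**What to change.** For the exposure outcome only:

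- Replace the bivariate screen with one pre-specified Firth-penalised (or exact) logistic model containing arm and at most one covariate named in advance. Smoking is a candidate, because the Background cites it as a consistent risk factor. The documents do not show whether the history form records it, so that needs checking first.
- Do not enter five site terms as ordinary covariates. Handle site by stratification, for example with a site-stratified Mantel-Haenszel risk difference or an exact conditional analysis as a supporting estimate.
- Report all other risk-factor comparisons for exposure as descriptive.

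The primary test, sample size and visits stay as they are. The cost is a change of wording in Statistical Methods and fewer exploratory risk-factor models for exposure.

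### The 80 per arm does not follow from a one-sided alpha of 0.10 (57 to 58 would), and the plan gives two conflicting rules for the primary test

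*Combined protocol and SAP*

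**What the plan says.** Under Sample Size, the plan takes exposure rates of 10% (permanent suture) and 1% (absorbable suture), 1:1 allocation and power 0.8, and concludes that "we will need to study 80 experimental subjects and 80 control subjects". On the error rate it says "The Type I error probability associated with the test of this null hypothesis is 0.1", and then "The alpha of 0.1 is based on a one-sided hypothesis", in the direction of more exposures with permanent suture. On the test it says "We will use an uncorrected chi-squared statistic to evaluate this null hypothesis". Enrolment is 200 in total to allow for 20% loss, and the section adds: "thus the use of chi square is appropriate given the adequately large sample size".

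Under Statistical Methods, the general rule is "chi-square or Fisher's exact for categorical data". It goes on to say that "both chi square and Fisher's exact analyses are performed" and that "the appropriate test and associated p value will be used based on the proportion of samples with input less than 5" percent of the total population; results with small counts go to Fisher's exact. The primary outcome is categorical, and nothing in that section exempts it.

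**The concern.** There are two faults. First, every input to the sample size is given, yet the stated answer does not follow from them. If the alpha is right, the power is misstated. If the power is right, the decision threshold is half the declared one. A reader cannot tell which threshold will decide the trial.

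Second, one section fixes the primary test and another leaves it to a rule applied to the data. The defence of chi-square rests on the number of participants, but the approximation depends on the number of events, and few are expected. If both p values are computed and the rule for choosing between them is unclear, the choice can be made after the results are known. The question is whether that choice could change the conclusion.

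**Working it through.** **Inputs (Sample Size section).** p1 = 0.10, p2 = 0.01, difference 0.09 (squared: 0.0081), 1:1 allocation, power 0.8 (z = 0.8416), alpha 0.10 described as one-sided, uncorrected chi-square. Mean rate 0.055, so 2 × 0.055 × 0.945 = 0.10395. Sum of the separate variances: 0.0900 + 0.0099 = 0.0999.

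**Formulas, n per arm.**
- Pooled: n = [z_alpha √0.10395 + 0.8416 √0.0999]² / 0.0081
- Simple (average variance): n = (z_alpha + 0.8416)² × 0.10395 / 0.0081

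**What reproduces the plan's 80.** One-sided 0.05, which is two-sided 0.10 (z = 1.6449):
- Pooled: (0.5303 + 0.2660)² / 0.0081 = 78.29
- Simple: (1.6449 + 0.8416)² × 0.10395 / 0.0081 = 79.34

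Rounded up, these are 79 and 80. The allowance for loss also reproduces: 160 / 0.8 = 200.

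**What the stated alpha gives.** One-sided 0.10 (z = 1.2816):
- Pooled: (0.4132 + 0.2660)² / 0.0081 = 56.95
- Simple: (1.2816 + 0.8416)² × 0.10395 / 0.0081 = 57.85

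So 57 to 58 per arm. Approximate power at 80 per arm is Φ[(0.09 √80 − 0.4132) / √0.0999] = Φ(1.240) = 89.2%. A continuity-corrected formula at one-sided 0.10 gives 77.6 to 78.5, close to 80, but the plan says the statistic is uncorrected.

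**Expected events.** At 80 per arm: 80 × 0.10 = 8 and 80 × 0.01 = 0.8, a mean of 4.4 per arm. At 100 per arm: 10 and 1, a mean of 5.5.

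**Exact results.** These come from enumerating both binomial distributions at 10% versus 1%. They differ from the normal approximation (94.4% rather than 89.2% for chi-square) because the events are few.

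| One-sided alpha | n per arm | Chi-square power | Fisher's power | Opposite conclusions |
|---|---|---|---|---|
| 0.10 | 80 | 94.4% | 84.8% | 9.6% |
| 0.10 | 100 | 97.3% | 92.6% | 4.7% |
| 0.05 | 80 | 89.1% | 75.2% | 13.9% (89.1 − 75.2) |

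Every disagreement has chi-square significant and Fisher's not. Example at 80 per arm: 5 versus 1 events gives one-sided p = 0.048 by chi-square and 0.105 by Fisher's, on opposite sides of 0.10.

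**The selection rule.** Its wording has no single meaning, so three readings were tried at one-sided 0.10. Fisher's is used if:
- (a) total events are below 5% of all participants;
- (b) expected events per arm are below 5;
- (c) the smaller event count is below 5% of all participants.

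| Reading | Fisher's chosen, n = 80 | Power of the rule, n = 80 | Differs from fixed chi-square, n = 80 | Fisher's chosen, n = 100 | Differs, n = 100 |
|---|---|---|---|---|---|
| a | 34% | 87.8% | 6.6% | 33% | 3.2% |
| b | 62% | 86.0% | 8.4% | 33% | 3.2% |
| c | nearly all | 84.8% | 9.6% | nearly all | 4.7% |

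**True size at nominal 10%, 80 per arm**, maximised over common rates from 0.1% to 50%: chi-square 12.2% (at a common rate of 2.3%), the rule 10.7% to 10.8%, Fisher's 8.0%. At a common rate of 5.5%, chi-square is 11.0% and Fisher's 4.7%.

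**The case against.** The strongest reply is that the error is on the safe side. At the declared alpha, 80 evaluable per arm gives more than 80% power under either test and under every reading of the rule, and a larger sample than needed does not invalidate a test. This stands, and it limits the harm.

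A second reply is that the alpha sentence may loosely mean a two-sided 0.10 chosen because the hypothesis is directional. That would reconcile the 80. But the text does not say so, and on that reading the declared one-sided level would still have to be corrected to 0.05. The software output that could settle it is not in the documents.

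Third, the Sample Size sentence refers specifically to the primary null hypothesis, and a specific rule can be read as overriding a general one. This is a fair reading, but neither section states it.

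Fourth, the disagreement rates depend on readings that had to be supplied for an unclear rule, on the planning rates, and on the number evaluable; at 100 per arm they are about half as large. The rule's maximum size under reading (c) occurs at a common rate near 37%, beyond the 0 to 27% range the plan cites; for common rates up to 10% it is about 6.4%. These limits are accepted.

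Finally, the preference for Fisher's is partly a matter of judgement. The excess size of chi-square is modest, and Fisher's gives up about 10 points of power at 80 per arm.

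**Conclusion.** The point holds and should be fixed. With the stated inputs, 57 to 58 per arm are needed, not 80, so either the power of 0.8 or the one-sided alpha of 0.10 is misstated. That a two-sided 0.10 was entered and then described as one-sided is the likeliest cause, but this is an inference.

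The primary test is also not uniquely defined. At one-sided 0.10 and rates of 10% and 1%, following Statistical Methods instead of Sample Size changes the conclusion in 6.6% to 9.6% of trials at 80 per arm and 3.2% to 4.7% at 100, depending on how the rule is read. The trial is not underpowered at the declared alpha. The check takes the one-sided test of a difference described under Sample Size; the non-inferiority wording under Primary Hypothesis is a separate matter.

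**What to change.** First choice: keep the declared one-sided 0.10 and 80 evaluable per arm, correct the stated power, and name one primary test that holds its level. Fisher's exact is already in the plan. Suggested text: *The primary outcome will be tested with a one-sided Fisher's exact test at alpha 0.10; with 80 evaluable participants per arm the exact power for 10% versus 1% is 85%. The test-selection rule in Statistical Methods does not apply to the primary outcome.*

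If the sponsor prefers the uncorrected chi-square, both sections should say so and disclose its exact power (94%) and its true size of up to 12.2% at 80 per arm.

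Only if the software output confirms that the calculation was two-sided 0.10 (one-sided 0.05): state that alpha, and replace 80% with the named test's exact power at 80 per arm, which is 75% for Fisher's or 89% for chi-square.

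Cost: at the declared alpha this is a text change with no added participants, since Fisher's reaches 80% power with 73 per arm. The price is lower power than chi-square: 85% instead of 94% at 80 per arm, and 93% instead of 97% at 100. In the one-sided 0.05 case the threshold becomes stricter than declared. Fisher's would then need 87 evaluable per arm for 80% power, which is 87 / 0.8 = 108.75, so 109 per arm or 218 enrolled, unless the sponsor accepts 75% at 80 evaluable (85% if all 100 per arm are evaluable). The choice should be fixed before any outcome data by arm are examined.

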The primary aim of this randomized trial, therefore, is to test the hypothesis that use of the Upsylon™ mesh with a delayed absorbable suture for mesh attachment at the time of robotic-assisted total laparoscopic hysterectomy and SCP will reduce the risk of vaginal

mesh and/or suture exposure rates compared to a permanent monofilament suture. Secondary aims will include an evaluation of the effect of this light-weight mesh and absorbable suture on prolapse and quality of life outcomes and surgical complications at 1 year after surgery.

STUDY DESIGN AND METHODS

This is a randomized controlled trial that will be conducted at 5 clinical sites:

1. The University of North Carolina, Chapel Hill
2. Northwestern Medical Center, Chicago
3. Augusta University, Augusta
4. Wake Forest Baptist Health, Winston-Salem
5. Carolinas Healthcare System, Charlotte

Human Subject Research & Informed Consent

Signed IRB approved consents will be obtained from each participant at the time of enrollment prior to any study-related assessments. The informed consent form will describe the study in detail, as well as the planned and permitted uses, transfers, and disclosures of the subject's personal health information. The objectives of the study and data collection will be explained to every prospective participant prior to enrollment. The participant will be given ample opportunity to inquire about details of the study to decide whether or not to participate. Copies of the informed consent form will be provided to the participant and original documents filed at each study center as per regulatory requirements.

Participants have the right to:

- Withdraw or refuse participation without prejudice at any time during the study
- Voluntarily participate in the study
- Understand the risks and benefits of the study
- Maintain confidentiality of personal medical information
- Receive new information about the study as it becomes available

Participant Screening & Point of Enrollment

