Statistical testing will be performed to determine if the incidence of mesh and suture exposure in the absorbable suture arm is non-inferior to the permanent suture arm. The null hypothesis is that the incidence of mesh and suture exposure in the absorbable suture arm will be equal to the incidence of mesh and suture exposure in the permanent suture arm.

Secondary Hypotheses

1. Statistical testing will be performed to determine if the composite success rate in the absorbable suture arm will be non-inferior to the permanent suture arm. The null hypothesis is that the success rate in the absorbable suture arm is less than or equal to the success rate in the permanent suture arm.
2. Statistical testing will be performed to determine if the symptomatic success rate in the absorbable suture arm is non-inferior to the permanent suture arm. The null hypothesis is that the success rate in the absorbable suture arm is less than or equal to the success rate in the permanent suture arm.
3. Statistical testing will be performed to determine if the AE incidences rate of the absorbable suture arm is non-inferior to the permanent suture arm. The null hypothesis is that the AE incidences rate in the absorbable suture arm is greater than or equal to the rate in the permanent suture arm.

STUDY MONITORING AND DOCUMENTATION

The Principle Investigator will monitor the study and assess the need for amendments as the study progresses. If a protocol revision is necessary for reasons including but not limited to the rights, safety or welfare of participants, or scientific integrity of the data, an amendment is required. Appropriate approvals (e.g., IRB) of the revised protocol must be obtained prior to implementation at each site.

Site Documentation

All study documents included in this protocol that will be presented to subjects will be submitted to the IRB for approval. Each site will maintain a site study binder that will include the following:

- Enrollment log of patients who have consented to be in the study (electronic version)
- Protocol Deviation Log (electronic version)
- Adverse Event Log (electronic version)
- Investigator protocol and amendments
- IRB submissions, modifications, renewals
- Data Coordinating Center monitoring correspondence
- DSMB reports
- IRB approved Informed Consent Form

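### Secondary hypotheses 1 to 3 are labelled non-inferiority but written as zero-margin superiority tests, so they cannot show non-inferiority when the sutures perform alike; the primary carries the same wrong label

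*Combined protocol and SAP*

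**What the plan says.** All four hypotheses under Statistical Considerations are announced as non-inferiority tests.

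- **Secondary 1 and 2.** The tests are to determine if "the composite success rate in the absorbable suture arm will be non-inferior to the permanent suture arm" and if "the symptomatic success rate in the absorbable suture arm is non-inferior to the permanent suture arm". The null given for each is that "the success rate in the absorbable suture arm is less than or equal to the success rate in the permanent suture arm".
- **Secondary 3.** The test is to determine if "the AE incidences rate of the absorbable suture arm is non-inferior to the permanent suture arm". Its null is that "the AE incidences rate in the absorbable suture arm is greater than or equal to the rate in the permanent suture arm".
- **Primary.** The test is to determine if "the incidence of mesh and suture exposure in the absorbable suture arm is non-inferior to the permanent suture arm". Its null is one of equal rates, with the wording "mesh and suture exposure in the absorbable suture arm will be equal to the incidence of mesh and suture exposure" (the comparator being permanent suture).

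Elsewhere the primary question is one of superiority. The Background closes with the hypothesis that a "delayed absorbable suture for mesh attachment at the time of robotic-assisted total laparoscopic hysterectomy and SCP will reduce the risk of vaginal" mesh or suture exposure. The Sample Size section assumes 1% against 10%, with a one-sided alternative that permanent suture is worse.

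The Statistical Methods section lists tests of difference (t-test, chi-square or Fisher). It mentions confidence intervals but no bound to compare them with. The only between-arm difference used to design a test is the 9-point effect on exposure. No alpha or power is stated for the secondary tests.

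**The concern.** A non-inferiority null says that the new treatment is worse by at least a stated margin. The secondary nulls say that absorbable suture is no better than permanent suture, so label and null ask different questions.

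This matters because of the trial's own rationale. The Background section on suture material wants a method of attachment that reduces mesh complications and keeps the prolapse repair effective. It notes that permanent suture was traditionally favoured to prevent recurrence and that no prospective study has settled the matter. Secondary hypotheses 1 and 2 are where the plan addresses that half of the question. The welcome result there is similar success, which is the case the written tests cannot confirm. A non-significant result reported under a non-inferiority heading could then be taken as reassurance.

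**Working it through.** **1. The plan's own figure.** Inputs from Sample Size: 10% v 1%, power 0.8, alpha 0.1, uncorrected chi-square, 80 per arm. The superiority formula is n = [z_α√(2p̄(1−p̄)) + z_β√(p₁q₁+p₂q₂)]²/d², with p̄ = 0.055 and d = 0.09.

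- One-sided 0.05 (the same as two-sided 0.10): (1.645×0.3224 + 0.842×0.3161)²/0.0081 = 78.3, so 79 per arm.
- One-sided 0.10: 57 per arm.

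The stated 80 is therefore a superiority calculation with no margin in it, and the primary design does not rest on the non-inferiority label. The gap between 57 and 79 is a separate question about alpha and sidedness. Enrolment: 160/0.8 = 200, or 100 per arm.

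**2. How often the written secondary tests find in favour when the arms are equal.** Exact enumeration over two independent binomials, with the one-sided pooled chi-square (reject when z ≥ z_α) or one-sided Fisher. The success rates are assumptions. Both alphas are shown because none is stated for these tests. Entries are for true success of 85 / 90 / 95%.

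| Evaluable per arm | Alpha (one-sided) | Chi-square, % | Fisher, % |
|---|---|---|---|
| 80 | 0.05 | 5.0 / 5.1 / 5.9 | 3.2 / 2.8 / 2.2 |
| 80 | 0.10 | 10.5 / 10.8 / 11.1 | 6.7 / 6.1 / 4.5 |
| 100 | 0.05 | 4.9 / 5.1 / 5.7 | 3.4 / 3.1 / 2.1 |
| 100 | 0.10 | 10.1 / 10.0 / 11.0 | 7.2 / 6.7 / 5.2 |

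For hypothesis 3 with truly equal adverse event rates of 10 to 40% and 80 per arm, the range is 4.7–5.1% or 10.0–10.8% by chi-square, and 2.8–3.6% or 6.1–7.9% by Fisher. A zero-margin test of equal arms rejects at about alpha or less, so more patients do not help.

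**3. What result would be needed (80 per arm).** Suppose permanent suture has 72/80 successes (90%).

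- Absorbable 78/80: z = 0.075/√(2×0.9375×0.0625/80) = 1.96, which passes at 0.05.
- Absorbable 77/80: z = 0.0625/√(2×0.93125×0.06875/80) = 1.56, which passes only at 0.10.
- Fisher needs 78/80 at either alpha.

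With 76/80 (95%) on permanent suture, chi-square needs 80/80 at 0.05 or 79/80 at 0.10. Fisher cannot reject at 0.05 and needs 80/80 at 0.10.

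**4. Direction of the error.** If absorbable suture is truly 10 points worse (80% v 90%, assumed; 80 per arm), the written chi-square rejects 0.03% of the time at 0.05 and 0.12% at 0.10. It is stricter than any non-inferiority test at the same alpha.

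**5. What non-significance tells us (80 per arm).** At one-sided 0.05 the written chi-square is non-significant 94–95% of the time with equal arms. It is non-significant over 99.7% of the time, at either alpha, when absorbable suture is 10 points worse. Even a two-sided 0.05 chi-square misses that loss 64.5 / 57.7 / 42.7% of the time (75 v 85, 80 v 90, 85 v 95%).

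**6. What a margin would offer.** Power = Φ(M/SE − z_α), with SE = √(2p(1−p)/n), equal arms, an assumed M of 10 points and one-sided 0.05. At 90% success and 80 per arm, SE = 0.0474 and Φ(2.108 − 1.645) = 68%.

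| Evaluable per arm | Success 85 / 90 / 95% | Adverse event rate 10 / 20 / 30 / 40% |
|---|---|---|
| 80 | 55 / 68 / 90% | 68 / 47 / 40 / 36% |
| 100 | 63 / 76 / 95% | 76 / 55 / 46 / 42% |

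Without a margin, the 95% interval for a difference in success has half-width 1.96√(2p(1−p)/80), or about 11.1 / 9.3 / 6.8 points at 85 / 90 / 95% success.

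**The case against.** The strongest reply is that little can go wrong. The written nulls are stricter than any non-inferiority null, they concern secondary endpoints only, and no sample size, stopping rule or primary test depends on them. That stands, and it limits the severity.

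Two further points stand. First, 80 per arm is the worst case: 100 per arm are planned, and women who miss the Year 1 visit can still contribute adverse events. The calculations therefore show both sizes. Second, Statistical Methods already brings confidence intervals into outcome assessment. However, its sentence starts from continuous data, is unclear for binary outcomes, and gives no decision bound.

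It can also be said that step 2 shows only that a level-alpha test rejects at about alpha. That is true, and it is the point: a test with this property is a poor means of confirming similarity.

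A reader might infer that the secondary tests can never show non-inferiority. They can, but only by showing superiority. A reader might also infer that the plan intends to treat non-significance as non-inferiority. It does not say so; it only sets no rule against it.

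**Conclusion.** The plan contradicts itself and should be corrected. Secondary hypotheses 1 to 3 promise a non-inferiority answer, and their nulls can give one only if absorbable suture is shown to be better. With equal arms the chance of a favourable conclusion is about 5–6% at one-sided 0.05 or 10–11% at 0.10 by chi-square, and about 2–3% or 4.5–7% by Fisher. These figures assume success of 85–95% and 80 to 100 evaluable per arm. The contradiction itself needs no assumed rate.

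The error does not inflate false claims. The harm is a probably inconclusive answer under a heading that invites a favourable reading.

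For the primary, the fault is the label alone. It would be wrong to infer that the primary test or sample size fails because of it: aim, assumed rates and calculation are all superiority. Equally, this does not clear the primary test of the separate questions on alpha and sidedness, and on chi-square against Fisher, in Statistical Methods and Sample Size.

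**What to change.** 1. **Primary.** Replace the non-inferiority wording with one-sided superiority. H0: exposure with absorbable suture is at least that with permanent suture. H1: it is lower.

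2. **Secondary 1 to 3.** Make label and null agree in one of two ways.
   - (a) Delete the non-inferiority label and report each risk difference with its confidence interval, stating that this covers binary outcomes. State that no non-inferiority claim will be made and that non-significance will not be read as equivalence. This fits the Secondary Aims, which are to compare and to evaluate.
   - (b) Before outcomes are compared by arm, pre-specify a clinically justified margin for each endpoint. State the null as worse by at least that margin, conclude from the confidence bound at a stated one-sided alpha, and state the power. This fits the Background's concern with keeping the repair effective.

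Under (b), base any durability claim on composite components a–c or on symptomatic success. Component d is exposure itself, and a gain there can hide a loss of support. Assuming independence and exposure of 1% v 10%, a 10-point loss on a–c (80% v 90%) becomes 0.80×0.99 = 79.2% v 0.90×0.90 = 81.0% on the composite, a loss of only 1.8 points.

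**Cost.** A wording amendment to the two hypothesis sections, with the usual IRB approvals at the five sites. No extra patients, visits or data are needed. Option (b) also needs a clinical justification for each margin.
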